### 6.2.1.2 Expansion Cohorts (Arm B) Regimen

Once the RP2D is determined from the dose finding cohort, 4 expansion cohorts will be enrolled on Arm B on this study as defined in **Section 6.4**. Expansion cohorts B1-B3 will receive a priming dose of Hu5F9-G4 (magrolimab) (1 mg/kg) on week 1, followed in week 2 with Hu5F9-G4 (magrolimab) administered at RP2D on Day 1 and dinutuximab 17.5 mg/m^2 on Days 2-5. Hu5F9-G4 (magrolimab) will be administered at RP2D on Day 1 of week 3 and 4. A maximum of 12 cycles (see Table 6) can be completed in the absence of DLT or disease progression.

Patients in Arm B Cohort B4 will be enrolled in two subgroups:

- 1. Those who are scheduled for resection of lung lesion(s) (preferred), or those who have recently undergone resection of lung lesion(s) will start the Hu5F9-G4 (magrolimab)/dinutuximab within four weeks of resection as outlined in Section 6.4 and Table 6, and
- 2. Those who are scheduled for resection of lung lesions in a stepwise fashion. Patients in this group will initiate treatment between resections as described in Section 6.4. Prior to resection all patients will receive the Hu5F9-G4 (magrolimab)/dinutuximab as outlined in Table 6. If restart of Hu5F9-G4 (magrolimab)/dinutuximab occurs within four (4) weeks of the last dose of Hu5F9-G4 (magrolimab), the patient will pick up the regimen as per the next scheduled regimen cycle for a maximum of 5 cycles postoperatively.
  - If the restart of the Hu5F9-G4 (magrolimab)/dinutuximab is delayed beyond four weeks of the last dose of Hu5F9-G4 (magrolimab), the post-surgical regimen will be conducted as per Table 7 and will require a re-priming dose of Hu59-G4 (magrolimab).

Every attempt will be made to enroll to the "step-wise resection" subgroup prior to the first resection in order to obtain tissue from the resection for research correlatives. If subjects are enrolled after the initial resection, a request will be made

\*\* Cycles may be repeated as long as the patient does not have unacceptable toxicity (see Section 6.3 or Section Error! Reference source not found.) or disease progression to a maximum of 12 cycles

^ Hydroxyzine (0.5-1 mg/kg, Max dose 50 mg) PO may substitute for diphenhydramine

for archived tissue for analysis. Within 4 weeks after the initial resection, patients will receive the priming dose of Hu5F9-G4 (magrolimab) on Day 1, followed by Cycle 1 in week 2 with Hu5F9-G4 (magrolimab) administered at RP2D on Day 1 and dinutuximab 17.5 mg/m² on Days 2-5, followed by Hu5F9-G4 (magrolimab) at RP2D on Day 1 of weeks 3 and 4 until the second resection (see Table 6 below). Upon recovery from the second resection, the cycles may be repeated to a maximum of 5 cycles (adjuvant therapy). If the cycles are restarted within 4 weeks of the last dose of Hu5F9-G4 (magrolimab), the patient will pick up the regimen as per the next scheduled regimen cycle as per Table 6. If restarting the regimen is delayed beyond 4 weeks of the last dose of Hu5F9-G4 (magrolimab), the patient will restart as per Table 7 and will require a re-priming dose of Hu59-G4 (magrolimab) with repeat of cycle 1 and 2 with weekly dosing of Hu5F9-G4 (magrolimab).

Table 6: Regimen Description for Arm B - Expansion Cohorts B1 - B3 (Confirmed Neuroblastoma, Evaluable Neuroblastoma, Measurable Osteosarcoma), Cohort B4 (Resectable, pulmonary only relapsed osteosarcoma\*\*) - Non-staged resections and Cohort B4 - Staged resections prior to surgery and post resection with restart within 4 weeks of last dose

Agent	Premedications; Precautions	Dose	Route	Schedule	Cycle Length
Hu5F9-G4 (magrolima b)	Administer according to guidelines in Section 6.2.1.3. Acetaminophen oral (PO) and diphenhydramine (IV) or a comparable regimen up to 15 minutes before the first two doses of Hu5F9-G4 (magrolimab), and in case	650 mg) of acetaminophen; 0.5 - 1 mg/kg (max 50 mg) of diphenhydrami	PO; Diphenhydramin	Priming: Day 1 Week 1	
	of re-priming of the patient after > 4 weeks interruption in treatment.	Hu5F9-G4 (magrolimab) 1 mg/kg	IV (peripheral or central line) over 3 hours (± 30 min)		
	Monitor for infusion reactions during and for 1-hour post infusion during the priming dose. Any patients experience AEs during this period should be monitored as clinically indicates for up to 24 hours post infusion. Treatment of infusion reactions will be according to standard operating procedures.	Hu5F9-G4 (magrolimab) RP2D mg/kg*	infusions: Infuse IV over 2 hours (± 10 min)	Cycle 1: Day 1, Weeks 2, 3 and 4 Cycle 2: Day 1, Weeks 1, 2 and 3 Cycle 3 and subsequent cycles: Day 1 of Weeks 1 and 3 of each cycle (Week 2 is skipped)**	21 days (3 weeks)
Dinutuxima b	Administration requires premedication (acetaminophen - oral, diphenydramine -IV, and analgesia) and hydration prior to initiation according	650 mg) of acetaminophen ; 0.5 - 1 mg/ kg (max 50 mg) of	PO Diphenhydramin e^ IV (no need to	Cycles 1 (Week 2): Days 2-5  Subsequent cycles: Days	

to Section 6.2.1.4	ne^	immediate	2-5 of the first
		follows previous	week of each
	Analgesia per	drug infusion)	subsequent
	section 6.2.1.4		cycle
		Analgesia as	
	_	described below	
	$17.5 \text{ mg/m}^2$	in Section	
		6.2.1.4 .	
Administer 0.9% Sodium Chloride Injection USP 10 mL/kg as an IV over 1 hour prior to initiating drug infusion		Dinutuximab in 100 mL bag of 0.9% Sodium Chloride Injection USP (mix by gentle inversion- DO NOT shake)	

\* Determined during dose finding cohort.

Table 7: Regimen Description for Arm B - Expansion Cohort B4 Staged Resection - Post Resection with Delayed Restart > 4 weeks (Resectable, pulmonary only relapsed osteosarcoma\*\*)

**Post-Surgical** resection for staged bilateral pulmonary metastases (regimen for at least 1 cycle prior to pulmonary metastesectomy) if restart delayed

Agent	Premedications; Precautions	Dose	Route	Schedule	Cycle Length
Hu5F9-G4 (magrolima b)	Administer according to guidelines in Section 6.2.1.3. Acetaminophen	650 mg) of acetaminophen; 0.5 - 1 mg/ kg (max 50 mg) of diphenhydramine^	n PO; Diphenhydrami ne IV  Priming: Infuse IV (peripheral	Post resection Priming: Day 1, Week 1	21 days (3 weeks)
	reactions during and for 1-hour post infusion during the priming dose. Any patients experience AEs during this period should be monitored as clinically indicates for up to 24 hours post infusion. Treatment of infusion reactions will be	Cycles 1-2: Hu5F9-G4 (magrolimab) RP2D mg/kg*	infusions:	Post resection Cycle 1: Day 1, Weeks 2, 3 and 4  Post resection Cycle 2: Day 1 of each week	

\*\* Cycles may be repeated as long as the patient does not have unacceptable toxicity (see **Section 6.3** or **Section** Error! Reference source not found.) or disease progression to a maximum of 12 cycles (in Cohorts B1 through B3) or to a maximum of 5 cycles post resection (Cohort B4)

^ Hydroxyzine (0.5-1 mg/kg, Max dose 50 mg) PO may substitute for diphenhydramine

	according to standard operating procedures.			Post resection Cycle 3 and subsequent cycles: Day 1 of Weeks 1 and 3 of each cycle (Week 2 is skipped)	
Dinutuxima b	premedication (acetaminophen - oral, diphenydramine -IV, and analgesia) and hydration prior to initiation according to Section 6.2.1.4  Administer 0.9% Sodium Chloride Injection USP 10	650 mg) of acetaminophen; 0.5 - 1 mg/ kg (max 50 mg) of diphenhydramine^  Analgesia per section 6.2.1.4  Dinutuximab -	n PO Diphenhydrami ne^ IV	resection cycles: Days 2-5 of the first week of each subsequent	

\* Determined during dose finding cohort.

### 6.2.1.3 Clinical Care for Administration of Hu5F9-G4 (magrolimab)

A priming dose of Hu5F9-G4 (magrolimab) is required on week 1, prior to starting therapy and upon restart of therapy if > four weeks occurs since the last dose of Hu5F9-G4 (magrolimab). The priming dose (1 mg/kg) will be infused over 3 hours (+/- 30 minutes) via a peripheral or central line. Protecting IV bag from light is not required. In-line IV filter set is not required. Subsequent IV doses can be infused over 2 hours (+/- 10 minutes). If Hu5F9-G4 (magrolimab) dosing is ever delayed for greater than 4 weeks, a re-priming dose must be administered on week one, with scheduled dosing restarted 1 week later as depicted in **Figure 2**.

\*\* Patients who are scheduled for resection of lung lesion(s) unilateral or those who have recently undergone resection of lung lesion may continue the regimen for up to 5 cycles post resection in the absence of unacceptable toxicity or disease progression/recurrence.

^ Hydroxyzine (0.5-1 mg/kg, Max dose 50 mg) PO may substitute for diphenhydramine

Hu5F9-G4 (magrolimab) dose will be calculated using the actual body weight of the patient at enrollment (screening visit), and the dose may remain constant throughout the study unless a greater than 10% change in weight is observed.

Hu5F9-G4 (magrolimab) may interfere with the assessment of RBC phenotyping. Hu5F9-G4 (magrolimab) binds to CD47 on RBCs and can mask detection of antibodies to minor antigens to the patient's RBC and ABO/Rh phenotype, DAT and Ab screen. Refer to section 7.2.4 for assessments to be performed and resulted prior to the administration of the priming dose.

Anemia is a known and well described risk for Hu5F9-G4, which can occur in early doses and is transient.

- Within 24 hours prior to the Priming dose (Week 1) of Hu5F9-G4 (magnolimab) infusion, all patients must have a documented hemoglobin level of  $\geq$  9.5 g/dL, per eligibility criterion 3.1.7.
- Within 24 hours prior to the first full dose (Week 2) of Hu5F9-G4 (magnolimab) infusion, all patients must have a documented hemoglobin level of  $\geq 9.0$  g/dL.
- Patients who do not meet these criteria must be transfused and have their hemoglobin rechecked to meet the minimum hemoglobin threshold, as noted above, prior to administrating each of the first 2 doses of Hu5F9-G4 (magrolimab).
- An additional hemoglobin must be checked 3 to 6 hours after the initiation of the first (Priming) and second (Week 2) doses of Hu5F9-G4 (magrolimab). The patient should be transfused as clinically appropriate. Investigators should consider additional hemoglobin monitoring during the first week of treatment in patients with symptoms of anemia or at increased risk of complications of anemia.

Men and women of reproductive potential must use effective contraception while receiving study treatment and for 4 months after the last dose of Hu5F9-G4 (magrolimab). Male patients whose partners are pregnant may continue study treatment and should use barrier method contraception (condom) to prevent exposing the fetus. Refer to Section 6.8 of for further details.

Since infusion reactions can occur, all patients should be monitored pre-priming dose (within 30 minutes), every 30 minutes (±10) during priming dose infusion, for 1-hour post-infusion of the priming dose with vital signs (heart rate, respiratory rate, blood pressure, temperature, pulse oximetry) or as clinically indicated. Vital signs and AEs will be collected 30 (±10) minutes and 1 hour (±10 minutes) post-infusion. Patients who experience any treatment-related adverse events during the observation period should be further monitored as clinically appropriate (e.g., for up to 24 hours post-dose). All patients should be monitored with hourly (±20 minutes) vital signs during and for 1-hour (±20 minutes) post-infusion for Cycle 1. Further doses (Cycle 2+) do not require post-infusion observation, but hourly (±20 minutes) vital signs during the infusion. Patients who experience any treatment-related AEs during the observation period should be further monitored as clinically appropriate.

### 6.2.1.4 Clinical Care for Administration Dinutuximab (Unituxin®)

Dinutuximab will be administered inpatient; ensure that cardiopulmonary resuscitation medications and equipment are available. Administer required premedication and hydration prior to initiation. Administer dose over 10-20 hours at an infusion rate initially at 0.875 mg/m²/hour for 30 minutes, or as per institutional guidelines. Infusion rates may be gradually increased as tolerated to a maximum rate of 1.75 mg/m²/hour, or as per institutional guidelines. The infusion duration may be extended up to 20 hours for anticipated toxicities (pain, fever, tachycardia, tachypnea, hypotension), not responding to other supportive measures, and the duration used should be recorded. The maximum infusion time is 20 hours; dinutuximab administration must be stopped after 20 hours even if the total dose has not been administered. The total dose given in 20 hours should be recorded.

• Analgesics for pain management

Administer analgesia and opioids as per institutional guidelines. As recommended, morphine sulfate (50 mcg/kg) should be

administered intravenously immediately prior to initiation of dinutuximab and then continue as a morphine sulfate drip at an infusion rate of 20 to 50 mcg/kg/hour titrated to effect during and for two hours following completion of dinutuximab, as per institutional guidelines.

Administer additional 25 mcg/kg to 50 mcg/kg intravenous doses of morphine sulfate as needed for pain up to once every 2 hours followed by an increase in the morphine sulfate infusion rate in clinically stable patients, or as per institutional guidelines.

Consider using fentanyl or hydromorphone if morphine sulfate is not tolerated, as per institutional guidelines.

If pain is inadequately managed with opioids or to reduce opiate requirements during dinutuximab therapy, consider use of gabapentin or lidocaine in conjunction with intravenous morphine or as per institutional guidelines.

To optimize the effect of gabapentin, it should be initiated 1 week prior to expected start of antibody so that it can be increased to full dose by the start of dinutuximab administration. Dosing should follow institutional standards; however, the following dosing may be considered:

- Day 1: 5 mg/kg/dose (max 300 mg/dose) at bedtime
- Day 2: 5 mg/kg/dose (max 300 mg/dose) BID
- Day 3: 5 mg/kg/dose (max 300 mg/dose) TID patients should be at this dose by the time of admission for cycle 1 dinutuximab
- Gabapentin doses can be increased further if necessary; institutional guidelines should be followed.

Lidocaine dosing should follow institutional standards; however, the following dosing may be considered:

- Initiate continuous infusion at 1 mg/kg/hour (bolus) with the continuous infusion rate of is 0.5 -2 mg/kg/hour.
- Lidocaine levels should initially be checked every 8 hours (Q8h) but may be spaced out once therapeutic concentrations have been achieved. Dose should be titrated in 25% increments to achieve therapeutic serum concentrations (goal 2-4 mcg/mL).
- Consider dose reduction in patients with hepatic disease.
- Premedications for infusion reactions
  - Antihistamines and Antipyretics

Administer an antihistamine such as diphenhydramine (0.5 to 1 mg/kg; maximum dose 50 mg) intravenously over 10 to 15 minutes starting 20 minutes prior to initiation of dinutuximab and as tolerated every 4 to 6 hours during the dinutuximab infusion, as per institutional guidelines.

Acetaminophen

Administer acetaminophen (10 to 15 mg/kg/dose; maximum dose 650 mg) PO approximately 20 minutes prior to each dinutuximab infusion and every 4 to 6 hours as needed for fever or pain, or as per institutional guidelines.

Ibuprofen

Administer ibuprofen (5 to 10 mg/kg/dose) every 6 hours as needed for control of persistent fever or pain, as per institutional guidelines.

• Monitoring Procedures

Vital signs (heart rate, respiratory rate, blood pressure, temperature, pulse oximetry) will be collected prior to the beginning of dinutuximab infusion (within 30 minutes) and every 30 (±10) minutes for the first hour of infusion, and then hourly during infusion, or as clinically indicated. Post-infusion, vital signs and AEs will be collected every 30 (±10) minutes twice, then hourly (±20) minutes for a total of 4 hours. For patients who previously tolerated the study agent without infusion-related reactions, the post-infusion monitoring period may be reduced at the discretion of and documented by the treating physician.

Document intake and output on the day of dinutuximab administration.

Standard imaging will be performed for disease assessment where indicated and according to the protocol schedule (screening, disease assessment at the conclusion of Cycle 2 and 4 and then every 4 cycles) (see Section 11).

# 6.3 Definition of Dose-Limiting Toxicity

Adverse events that occur within the first 21 days of the 'single agent Lead-In' dosing of Hu5F9-G4 (magrolimab) or during the 21 days of Cycle 1 during the combination Hu5F9-G4 (magrolimab) and dinutuximab drug infusions, are *at least possibly related* to at least 1 study agent, and are  $\geq$  *Grade 3 in severity* will be considered DLTs with the following additional criteria or exceptions:

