3	Sample Banking		Sample banking for future study	Frozen tumor tissue (when available)	1) Available archival tissue  2) Pulmonary Metastases resected from staged resection at enrollment and then after one cycle of protocol therapy (cohort B4 only)  3) Clinical biopsies obtained during therapy or at disease progression	Optional	EET Biobank

Priority	Biomarker Name	Assay (CLIA: Y/N)	Use in the Trial (Integral, Integrated, or Exploratory) AND Purpose	Specimens Tested	Collection Time Points	Mandatory or Optional	Assay Laboratory and Lab PI
4	CyTOF for immune subsets	Mass Cytomet ry CLIA: N	Exploratory  To determine changes in the peripheral immune subsets as a result of treatment with anti-CD47 / anti-GD2	marrow in	1) Baseline 2) Disease restaging (cycle 2, 4, 8, 12) 3) End of therapy	1) Nandatory (fresh or viably frozen) 2) Nandatory 3) Coptional	.edu
5	Sample Banking		Sample banking for future study	Mononucle arcells and plasma from bone marrow in Sodium Heparin and EDTA tubes (Bilateral)	Baseline if available  Disease restaging (cycle 2, 4, 8, 12)  End of therapy	Optional	EET Biobank
Blood-b	ased Biomark	ers		•			
1	Magrolimab PK	ELISA CLIA: N No Review Require d	Integrated Assess the drug concentrations achieved during this first in child trial	Serum from Red top tube	Safety lead-in D1, 8, 15 Cycle 1, D1, 8, 15, ARM B only: D22 Cycle 2, D1 Cycle 3, D1 Cycle 5, D1 Cycle 7, D1 Cycle 9, D1 Cycle 11, D1 End of therapy (all samples drawn prior to magrolimab infusion)	M (safety cohort and first three patients on any expansion cohorts)	PPD

Version Date: 02/02/2024

Priority	Biomarker Name	Assay (CLIA: Y/N)	Use in the Trial (Integral, Integrated, or Exploratory) AND Purpose	Specimens Tested	Collection Time Points	Mandatory or Optional	Assay Laboratory and Lab PI
2	Magrolimab anti-drug antibody (ADA) Testing	ECLIA CLIA: N No Review Require d	Integrated Assess for immune responses against magrolimab	Serum from Red top tube	Safety lead-in D1  Cycle 1, D1  Cycle 2, D1  Cycle 3, D1  Cycle 5, D1  Cycle 7, D1  Cycle 9, D1  Cycle 11, D1  End of therapy  (all samples drawn prior to magrolimab infusion)	M (safety cohort and first three patients on any expansion cohorts)	PPD

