3	FcR receptor polymorphis m	RT-PCR CLIA: N No Review Require d	Exploratory Assess contribution of FcR polymorphisms to disease response	PBMC from EDTA tube	Baseline: Arm A: Safety Lead In-Week 1, D1 Arm B: Cycle 1, D1	Optional	[name] Laboratory, University of Wisconsin) [name] [name]
4	KiR phenotyping	RT-PCR CLIA: N No Review Require d	Exploratory Assess contribution of KiR mismatching to disease response	PBMC from EDTA tube	Baseline: Arm A: Safety Lead In-Week 1, D1 Arm B: Cycle 1, D1	Optional	[name] Laboratory, University of Wisconsin [name] [name]

Priority	Biomarker Name	Assay (CLIA: Y/N)	Use in the Trial (Integral, Integrated, or Exploratory) AND Purpose		Collection Time Points	Mandatory or Optional	Assay Laboratory and Lab PI
5	HACA antibody testing	ELISA CLIA: N No Review Require d	Exploratory  Assess contribution of Human anti- chimeric antibody response to disease response		ARM A: Cycle 1: Day 1, 5  ARM B: Cycle 1: Day 8, 12  Cycle 2: Day 1 and 5  Cycle 4: Day 1 and 5  End of therapy	Mandatory	[name] Laboratory, University of Wisconsin [name] [name]
6	Luminex for peripheral cytokines	Lumine x CLIA: N No Review Require d	Exploratory  To assess for the presence of human cytokines	In HIII A	Safety Lead-In and Cycles 1-2: Weekly prior to magrolimab infusion  Subsequent cycles: Day 1 prior to infusion  End of therapy	Mandatory	Stanford Human Immune Monitoring Center (HIMC) [name] [name]
7	CyTOF for peripheral immune subsets	Mass Cytomet ry CLIA: N No Review Require d	Exploratory  To determine changes in the peripheral immune subsets as a result of treatment with anti-CD47/anti-GD2	in Sodium	Safety Lead-In and Cycles 1-2: Weekly prior to magrolimab infusion  Subsequent cycles: Day 1  End of therapy	Mandatory	Stanford Cancer Correlative Science Unit (CCSU) [name] [name]

This protocol is for research purposes only, see page 1 for usage policy

Priority	Biomarker Name	Assay (CLIA: Y/N)	(Integral,	the Trial Integrated, ratory) AND	Tested	Collection Time Points	v	Assay Laboratory and Lab PI
8	Sample Banking		Sample ba future stud	_	PBMCs from blood in EDTA	cycles 1-2: Weekly prior to magrolimab	Mandatory (bank cells when plasma is collected for cytokines)	EET Biobank

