### **6.4** Dose Expansion Cohorts

Upon determining RP2D, enrollment to 4 expansion cohorts will proceed to evaluate evidence of clinical activity (cohorts B1-3) and safety/feasibility of using this combination drug approach after surgery (cohort B4) (Figure 2).

Cohort B1 – Confirmed neuroblastoma: measurable neuroblastoma/ganglioneuroblastoma

Cohort B2 – Evaluable neuroblastoma

Cohort B3 – Measurable osteosarcoma

Cohort B4 – Resectable, pulmonary only relapsed osteosarcoma

All subjects will receive the priming dose of 1 mg/kg Hu5F9-G4 (magrolimab) on Day 1 of week 1. On Day 1 of week 2, subjects will receive Hu5F9-G4 (magrolimab) at RP2D followed by 17.5 mg/m² dinutuximab IV on Days 2-5. Then, they will receive Hu5F9-G4 (magrolimab) at RP2D on Day 1 of week 3 and week 4 (**Figure 2** and **Section 6.2.1.2**).

Cycle 2 will consist of Hu5F9-G4 (magrolimab) at RP2D on Day 1 of week 1 in combination with 17.5 mg/m² dinutuximab IV given on Days 2-5, followed by Hu5F9-G4 (magrolimab) at RP2D on Day 1 of weeks 2-3 (see **Figure 2** and **Section 6.2.1.2**). A disease evaluation will be conducted after Cycle 2 and Cycle 4, and then after every 4 cycles (every 12 weeks) until progressive disease or a maximum of 12 cycles (except cohort four which will have a maximum of five cycles after the patient is rendered No Evidence of Disease (NED)). After Cycle 2, each subsequent cycle will consist of Hu5F9-G4

(magrolimab) administered on Day 1 of weeks 1 and 3 of the cycle (week 2 will be a week of rest), with dinutuximab administration on Day 2-5 of week 1.

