## Total Infusion Volume per Age Group

Age Group	\ \ /	Maintenance Infusion Volume (mL) – infused over 2 hours (+/- 10 minutes)
≥1 year to < 2 years	50	100
2 years to < 6 years	250	250
6 years to < 12 years	250	250
12 years to < 18 years	250	500
Adult	250	500

The prepared IV solution can be stored at  $25^{\circ}$  C and must be used within 8 hours of preparation. Discard the prepared IV solution if exceeding 8 hours. Do not refrigerate the prepared IV solution. There is no stability data to support the prepared IV solution stored at  $2^{\circ}$ C -  $8^{\circ}$ C ( $36^{\circ}$  F to  $46^{\circ}$  F).

Do not mix with any other drug in the infusion bag or administration set.

Storage: Store vials at 2°C - 8°C (36° F to 46° F) in the original carton, protected from light. Do not freeze.

If a storage temperature excursion is identified, promptly return Hu5F9-G4 (magrolimab) to 2°C -8°C (36° F to 46° F) and quarantine the supplies. Provide a detailed report of the excursion (including documentation of temperature monitoring and duration of the excursion) to [contact] for determination of suitability.

**Stability:** Shelf-life stability studies of the intact or unused vials are on-going.

*CAUTION:* The single-use injectable vial contains no antibacterial preservatives. Therefore, it is advised that the reconstituted product be discarded 8 hours after initial entry.

**Route of Administration:** Intravenous. Do not administer as an IV bolus.

**Method of Administration:** A priming dose of Hu5F9-G4 (magrolimab) is required in Cycle 1 Day 1. The priming dose (1 mg/kg) will be infused over 3 hours (+/- 30 minutes) via a peripheral or central line. Protecting IV bag from light is not required. In-line IV filter set is not required. Subsequent IV doses are to be infused over 2 hours (+/- 10 minutes).

**Patient Care Implications:** Advise men and women of reproductive potential to use effective contraception while receiving study treatment and for 4 months after the last dose of Hu-5F9. Male patients whose partners are pregnant may continue study treatment and should use barrier method contraception (condom) to prevent exposing the fetus. Refer to the protocol Section 6.8 for specific guidance.

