Correlative Exploratory Biol	logy Studies										
Tumor tissue specimen 	X	X - As available									
Blood samples 		X	X	X	X	X	X	X	X		
Bone marrow aspirate 	X	→	→ End of Cycle 2, 4, 8 and 12					8 and 12	X		

Arm B patients will receive the priming dose followed by Cycle 1 and 2 (each 21 days). Cycles may be repeated as long as the patient does not have unacceptable toxicity (see Section 6.3 or Section Error! Reference source not found.) or disease progression to a maximum of 12 cycles for patients in cohorts B1, B2 and B3 and to a maximum of 5 cycles post resection for patients in cohort B4.

Standard medical history is acceptable. Following screening, updates to medical history should be recorded.

Prior and concomitant medications – All medications taken within 21 days prior to treatment initiation and all new medications, including all medications for AEs, taken up to 30 days after treatment discontinuation should be recorded.

Hu5F9-G4 (magrolimab) will be administered as a priming dose, single agent Safety Lead-In and Day 1 of every week of every 3 week Cycles as outlined in Section 6.2. A premedication regimen (oral acetaminophen and diphenhydramine, or comparable regimen) is required before the initial doses of Hu5F9-G4 (magrolimab) and in case of re-priming of the patient after > 4 weeks interruption in treatment.

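### As the regimen text numbers Cycle 1, the DLT window leaves out the Arm B priming week, although the same priming dose is counted in original Arm A patients

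*Combined protocol and SAP*

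**What the plan says.** Section 6.3 gives two periods in which a DLT can occur: the first 21 days of single-agent lead-in dosing, "or during the 21 days of Cycle 1 during the combination Hu5F9-G4 (magrolimab) and dinutuximab drug infusions".

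For Arm B, the regimen text puts priming before Cycle 1:

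- Section 6.4: "All subjects will receive the priming dose of 1 mg/kg Hu5F9-G4 (magrolimab) on Day 1 of week 1". The first full dose and dinutuximab follow in week 2, and then "they will receive Hu5F9-G4 (magrolimab) at RP2D on Day 1 of week 3 and week 4".
- Table 6 lists priming separately and gives the magrolimab schedule as "Cycle 1: Day 1, Weeks 2, 3 and 4".
- The Arm B calendar footnote in Section 11 says "Arm B patients will receive the priming dose followed by Cycle 1 and 2 (each 21 days", and the calendar gives priming its own column.

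Section 6.4 ties Arm B DLT monitoring to Cycle 1. Section 6.1.1.2 has the first three Arm B patients evaluated for DLT, and Section 9.2.1 says that establishing the safety of the combination is completed in them.

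Other places number the same weeks differently:

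- Section 8.1.1: "A priming dose of Hu5F9-G4 (magrolimab) is required in Cycle 1 Day 1".
- Table 2, pharmacokinetics: "Cycle 1, D1, 8, 15, ARM B only: D22".
- Table 2, HACA: "ARM B: Cycle 1: Day 8, 12".
- The Arm B pharmacokinetic worksheet (Appendix H) lists a priming day and then Cycle 1 Days 1, 8, 15 and 22.

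**The concern.** DLT is the endpoint behind the recommended phase 2 dose. In original Arm A patients the priming dose falls inside the 21-day lead-in (Section 11, Arm A footnote), so a qualifying event in that week counts. In Arm B the same 1 mg/kg dose falls outside the window, and no reason is given for the difference.

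The priming week is a plausible time for qualifying events: Section 7.2.1 says infusion reactions occur mainly with the first two magrolimab doses. The clearest case is a Grade 4 reaction at priming. Section 7.2.1 ends treatment for it, and the infusion-reaction exemption in Section 6.3 covers Grade 3 only. It would be a DLT in an original Arm A patient but not in Arm B. At stake are the reading of the first three Arm B patients and the Section 6.4 trigger for discussing the dose again. People working from different sections may also count different events.

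**Working it through.** **Inputs.** Window: Section 6.3. Arm B doses: Table 6 and Section 6.4, priming on Day 1 of week 1 and full doses on Day 1 of weeks 2, 3 and 4. Cycle length of 21 days: Table 6 and Section 11. Enrollment: Section 9.3.3.

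**1. Dose days.** Study day = 7 × (week − 1) + 1, which gives days 1, 8, 15 and 22.

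**2. The plan's own figure.** Cycle 1 in Table 6 is weeks 2 to 4, days 8 to 28. Length = 28 − 8 + 1 = 21 days, as stated.

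**3. What each numbering covers in Arm B.**

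| Numbering | Days in Cycle 1 | Doses inside | Dose outside |
|---|---|---|---|
| Table 6, 6.4, Section 11 | 8–28 (21 days) | 8, 15, 22 | 1 (priming) |
| 8.1.1, priming on Cycle 1 Day 1, held to 21 days | 1–21 | 1, 8, 15 | 22 |
| Table 2, if Cycle 1 starts at priming and includes Day 22 | 1 to at least 22 | 1, 8, 15, 22 | none, but longer than 21 days |
| Appendix H | Priming, then Days 1, 8, 15 and 22 | five sample points for four doses | fits none of the above |

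Days 1 to 22 inclusive are 22 − 1 + 1 = 22 days, so no 21-day window holds all four doses. The first row has the clearest support in the regimen text. Under it, days 1 to 7 are uncounted: 7 of 28 days (25%).

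**4. Original Arm A patients.** Priming and lead-in cover days 1 to 21 (doses on 1, 8 and 15). Cycle 1 covers days 22 to 42 (doses on 22, 29 and 36). All six doses are counted.

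**5. Who is affected.** Arm B can hold 3 × 20 + 10 = 70 of 82 patients (85%), including the first three.

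**6. Effect on the rules.** One uncounted event among the first three turns 1/3 into 0/3; Section 6.1.1.2 sets no threshold there. One uncounted event plus one Cycle 1 DLT turns 2/6 into 1/6, and the Section 6.4 trigger does not fire.

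**7. Illustration on assumed inputs.** None of these rates is in the documents. Let p be the 28-day DLT risk and f the share of DLT patients whose only qualifying event starts in the uncounted week. With q = p(1 − f), the chance of at least 2 in 6 is 1 − (1 − q)^6 − 6q(1 − q)^5.

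| p | f = 0 | f = 0.10 | f = 0.25 | f = 0.50 |
|---|---|---|---|---|
| 0.20 | 0.345 | 0.296 | 0.224 | 0.114 |
| 0.30 | 0.580 | 0.513 | 0.406 | 0.224 |
| 0.40 | 0.767 | 0.699 | 0.580 | 0.345 |

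The loss is small if few events fall in the priming week and large if half do.

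**The case against.** The best defense starts from Table 2. Read alone, it gives Arm B a Cycle 1 that starts at priming and runs to at least Day 22. Section 6.4 monitors DLTs in Cycle 1 without naming a number of days, so on that reading nothing is missed. This stands as far as it goes: a reader might infer that one of the four doses is lost under every numbering, and the documents do not support that. But the reading contradicts the 21 days in Sections 6.3 and 11 and the dosing weeks in Table 6, so it replaces the gap with a conflict.

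Second, the same single-agent priming dose is already DLT-assessed in original Arm A patients, and priming is 1 mg/kg at both dose levels, so it cannot separate them. Section 2.1.6 also reports 401 patients treated with magrolimab and a solid-tumor regimen that includes this priming dose. All of this is true and limits the harm. It does not explain why the same event is a DLT in one arm and not in the other.

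Third, no event is lost from safety review. Every treated patient is evaluable for toxicity (Section 9.2.1), and data are monitored in real time (Section 6.4). A priming-related event that starts on day 8 or later still counts. Most anemia is exempt in any case. This stands too: the gap concerns onset in days 1 to 7 and the DLT label only.

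Finally, a reader might infer that Arm A replacements who go from priming directly to Cycle 1 certainly have the same gap, and that such events would be removed by another replacement. Section 9.2.1 does not say what happens to a patient who stops between priming and Cycle 1, and the Arm A worksheets label that dose as part of the lead-in. The gap is possible there but not established.

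**Conclusion.** The concern holds for Arm B. Under the numbering in Table 6, Section 6.4 and Section 11, a related, non-exempt event of Grade 3 or higher that starts on study days 1 to 7 is outside the Section 6.3 window, and no other text brings it back in. This applies to up to 70 of 82 patients, including the three in whom safety of the combination is to be completed. The sections that number Cycle 1 differently do not close the gap; they conflict with the 21 days in Section 6.3.

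The conclusion rests on taking the regimen tables and calendar as the definition of Cycle 1. It does not show that the dose decision would be wrong: the documents give no rate of qualifying priming-week events, the three-patient step has no threshold, and the Section 6.4 trigger leads only to a discussion. For Arm A replacements without a lead-in, the text leaves the matter open. This should be fixed because it changes how the primary endpoint is counted and the correction is cheap.

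**What to change.** - In Section 6.3, for patients without a lead-in, define the DLT window as running from the priming dose to the end of the 21 days that start with the first full magrolimab dose. On the Arm B schedule this is 28 days and holds all four doses. Defining it by doses makes it independent of cycle labels.
- Refer to this window in Section 6.1.1.2 (first three Arm B patients) and Section 6.4 (ongoing monitoring and trigger).
- State in Section 9.2.1 that a patient who stops for a qualifying event in the window counts as a DLT and is not replaced. This also settles the case of Arm A replacements who skip the lead-in.
- Reconcile the Cycle 1 day numbering across Section 6.3, Table 6, Section 8.1.1, Table 2, Section 11 and the Arm B worksheets. Which numbering to keep is for the sponsor; no dosing day needs to change.

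The cost is wording and labels, since adverse events are already collected continuously. The Arm B confirmation is not delayed: Section 6.1.1.2 already requires 21 days after Cycle 1 in the final patient, which is day 28 + 21 = 49, or 21 + 21 = 42 if Cycle 1 starts at priming. Both are later than day 28. The drawback is that slightly more DLTs may be counted, and priming events say nothing about the difference between dose levels.
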